9.3.2. Unsolicited Adverse Events

Vaccine-related unsolicited AEs from the first study vaccination through 28 days post second vaccination will be coded by Medical Dictionary for Regulatory Activities (MedDRA®) for preferred term and system organ class (SOC) ([Table 27](#)). These AEs will be summarized as number and percentage of subjects reporting at least one event in each MedDRA® preferred term and SOC, cross tabulated by severity grade (none, mild, moderate, severe). Corresponding results for all unsolicited AEs will be presented by study arm as shown in [Table 28](#). A categorization by severity and vaccine-relatedness by study arm will be provided as provided in [Table 29](#). Subject-level unsolicited adverse events will be provided as shown in [Listing 10](#).

9.4. Deaths, Serious Adverse Events and other Significant Adverse Events

The number of SAEs and vaccine-related Medically Attended Adverse Events (MAAEs) through 6 months post first vaccination will be reported by detailed listings showing the event description, preferred term and SOC, relevant dates (study vaccinations and AEs), severity, vaccine-relatedness, and outcome for each event ([Table 30](#) and [Table 31](#)). Non-serious, unsolicited, moderate or severe adverse events will be listed as shown in [Table 32](#).

Unsolicited events will be visualized according to [Figure 5](#), [Figure 6](#), [Figure 7](#), [Figure 8](#), [Figure 9](#), [Figure 10](#), [Figure 11](#), and [Figure 12](#) and details will be provided according to [Listing 12](#).

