- **Moderate (Grade 2):** Events result in a low level of inconvenience or concern with therapeutic measures. Moderate events may cause some interference with functioning and daily activities.
- **Severe (Grade 3):** Events interrupt the subject's daily activities and may require systemic drug therapy or other treatment. Severe events are usually incapacitating.

Changes in the severity of an AE should be documented to allow an assessment of the duration of the event at each level of intensity to be performed. Adverse events characterized as intermittent require documentation of onset and duration of each episode.

Relationship to Study Products: The assessment of the relationship of an AE to the administration of study product is made only by those with the training and authority to make a diagnosis and listed on the Form FDA 1572 as an investigator based on all available information at the time of the completion of the eCRF. Whether the AE is related or not, is not a factor in determining what is or is not reported in this trial. If there is any doubt as to whether a clinical observation is an AE, the event should be reported.

In a clinical trial, the study product must always be suspect. To help assess, the following guidelines are used.

- Related – There is a reasonable possibility that the study product caused the adverse event. Reasonable possibility means that there is evidence to suggest a causal relationship between the study product and the adverse event.
- Not Related – There is not a reasonable possibility that the administration of the study product caused the event.

Medically Attended Adverse Event (MAAE): For each unsolicited AE experienced, the subject will be asked if he/she had received medical attention, defined as hospitalization, an emergency room visit, or an otherwise unscheduled visit to or from medical personnel for any reason. AEs characterized by such unscheduled medical care will be designated as MAAEs.

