9.2.3. Serious Adverse Events

Serious Adverse Event (SAE): An adverse event or suspected adverse reaction is considered “serious” if, in the view of either the investigator or sponsor, it results in any of the following outcomes:

- Death,
- a life-threatening adverse event¹,
- inpatient hospitalization or prolongation of existing hospitalization,
- a persistent or significant incapacity or substantial disruption of the ability to conduct normal life functions, or
- a congenital anomaly/birth defect.
- Important medical events that may not result in death, be life-threatening, or require hospitalizations may be considered serious when, based upon appropriate medical judgment they may jeopardize the patient or subject and may require medical or surgical intervention to prevent one of the outcomes listed in this definition. Examples of such medical events include allergic bronchospasm requiring intensive treatment in an emergency room or at home, blood dyscrasias or convulsions that do not result in inpatient hospitalization, or the development of drug dependency or drug abuse.

¹ Life-threatening adverse event. An adverse event is considered “life-threatening” if, in the view of either the site principal investigator or sponsor, its occurrence places the patient or subject at immediate risk of death. It does not include an adverse event, had it occurred in a more severe form, might have caused death.

SAEs will be:

- Assessed for severity and relationship to study product and alternate etiology.
- Recorded on the appropriate SAE data collection form and eCRF.
- Followed through resolution.
- Reviewed and evaluated by an Independent Safety Monitor (ISM) (as deemed necessary), the SMC (periodic review unless related), DMID, and the IRB.

9.2.4. Procedures to be Followed in the Event of Abnormal Laboratory Test Values or Abnormal Clinical Findings

The site principal investigator or appropriate sub-investigator is responsible for recording all AE/SAEs/MAAEs that are observed or reported during this trial, regardless of the relationship to study product. AE/SAEs/MAAEs, abnormal laboratory test values, or abnormal clinical findings will be collected, assessed, documented, reported, and followed appropriately.

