3.2. Study Outcome Measures

3.2.1. Primary

- Frequency and severity of solicited local and systemic reactogenicity from the time of study vaccine administration through 7 days post-vaccination.
- Frequency and severity of vaccine-related unsolicited adverse events (AEs) from the first study vaccination through 28 days post second vaccination.
- Frequency and severity of clinical safety laboratory AEs from the time of first study vaccination through approximately 28 days after the second vaccination.
- Frequency of Serious Adverse Events (SAEs) and vaccine-related Medically Attended Adverse Events (MAAEs) through 6 months post first vaccination.

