4.5.1. Safety Variables

Safety will be assessed by the occurrence of:

1. Serious adverse events and MAAEs occurring from the time of study vaccination through approximately 6 months after the first study vaccination.
2. Solicited Adverse Events – reactogenicity events occurring from the time of study vaccination through 7 days after each study vaccination:
 - a) Local AEs including pain, tenderness, erythema (redness), induration (hardness/swelling), ecchymosis (bruising) and pruritis (itching).
 - b) Systemic AEs including fever, feverishness (chills, shivering, sweating), fatigue (tiredness), malaise (general unwell feeling), myalgia (body aches/muscular pain), nausea, loss of appetite and headache.
3. Clinical safety laboratory adverse events occurring from the time of study vaccination through approximately 28 days after the second vaccination. Parameters to be evaluated include WBC, Hgb, platelet count, ANC, sodium, potassium, Creatinine, BUN (BUN will be obtained only if creatinine is above the normal range), and ALT.
4. Unsolicited Adverse Events – study vaccine-related non-serious adverse events occurring from the time of study vaccination through approximately 28 days after the second study vaccination.

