14.3 Safety Data

14.3.1 Displays of Adverse Events

Table 23: Overall Summary of Adverse Events

	Study Arm 1 ChAd3+Placebo (N=X)		Study Arm 2 ChAd3+ChAd3 (N=X)		Study Arm 3 ChAd3+MVA-BN (N=X)		All Subjects (N = X)	
Subjects* with	n	n%	n	%	n	%	n	%
At least one local solicited adverse event	x	x.x	x	x.x	x	x.x	x	x.x
At least one systemic solicited adverse event	x	x.x	x	x.x	x	x.x	x	x.x
At least one laboratory adverse event	x	x.x	x	x.x	x	x.x	x	x.x
At least one vaccine-related unsolicited adverse event	x	x.x	x	x.x	x	x.x	x	x.x
Mild (Grade 1)	x	x.x	x	x.x	x	x.x	x	x.x
Moderate (Grade 2)	x	x.x	x	x.x	x	x.x	x	x.x
Severe (Grade 3)	x	x.x	x	x.x	x	x.x	x	x.x
At least one serious adverse event [†]	x	x.x	x	x.x	x	x.x	x	x.x
At least one vaccine-related medically attended adverse event [§]	x	x.x	x	x.x	x	x.x	x	x.x

N = Number of subjects in the Safety Population. *: Subjects are counted once for each category regardless of the number of events. [†]: A listing of Serious Adverse Events is included in Table 28. [‡]: As reported on the Adverse Event eCRF. [§]: All vaccine-related medically attended adverse events are included in Table 29.

14.3.1.1 Solicited Adverse Events**Table 24: Number and Percentage of Subjects Experiencing Solicited Events with 95% Confidence Intervals by Symptom, Dose, and Treatment Group**

Symptom	Post Dose 1 Study Arm 1,2,3 ChAd3 (N=X)*			Post Dose 2 Study Arm 1 ChAd3+Placebo (N=X)			Post Dose 2 Study Arm 2 ChAd3+ChAd3 (N=X)			Post Dose 2 Study Arm 3 ChAd3+MVA-BN (N=X)			Post Either Dose Study Arm 1 ChAd3+Placebo (N=X)			Post Either Dose Study Arm 2 ChAd3+ChAd3 (N=X)			Post Either Dose Study Arm 3 ChAd3+MVA-BN (N=X)		
	n	%	95% CI†	n	%	95% CI†	n	%	95% CI†	n	%	95% CI†	n	%	95% CI†	n	%	95% CI†	n	%	95% CI†
Any Symptom	x	x.x	x.x, x.x	x	x.x	x.x, x.x	x	x.x	x.x, x.x	x	x.x	x.x, x.x	x	x.x	x.x, x.x	x	x.x	x.x, x.x	x	x.x	x.x, x.x
Any Systemic Symptom	x	x.x	x.x, x.x	x	x.x	x.x, x.x	x	x.x	x.x, x.x	x	x.x	x.x, x.x	x	x.x	x.x, x.x	x	x.x	x.x, x.x	x	x.x	x.x, x.x
Elevated Oral Temperature	x	x.x	x.x, x.x	x	x.x	x.x, x.x	x	x.x	x.x, x.x	x	x.x	x.x, x.x	x	x.x	x.x, x.x	x	x.x	x.x, x.x	x	x.x	x.x, x.x
Feverishness	x	x.x	x.x, x.x	x	x.x	x.x, x.x	x	x.x	x.x, x.x	x	x.x	x.x, x.x	x	x.x	x.x, x.x	x	x.x	x.x, x.x	x	x.x	x.x, x.x
Malaise	x	x.x	x.x, x.x	x	x.x	x.x, x.x	x	x.x	x.x, x.x	x	x.x	x.x, x.x	x	x.x	x.x, x.x	x	x.x	x.x, x.x	x	x.x	x.x, x.x
Fatigue	x	x.x	x.x, x.x	x	x.x	x.x, x.x	x	x.x	x.x, x.x	x	x.x	x.x, x.x	x	x.x	x.x, x.x	x	x.x	x.x, x.x	x	x.x	x.x, x.x

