Any SOC	Any PT	Any Severity	x	x.x	x	x.x	x	x.x	x	x.x	x	x.x	x	x.x	x	x.x	x	x.x	x	x.x
		Mild	x	x.x	x	x.x	x	x.x	x	x.x	x	x.x	x	x.x	x	x.x	x	x.x	x	x.x
		Moderate	x	x.x	x	x.x	x	x.x	x	x.x	x	x.x	x	x.x	x	x.x	x	x.x	x	x.x
		Severe	x	x.x	x	x.x	x	x.x	x	x.x	x	x.x	x	x.x	x	x.x	x	x.x	x	x.x
SOC 1	PT 1	Any Severity	x	x.x	x	x.x	x	x.x	x	x.x	x	x.x	x	x.x	x	x.x	x	x.x	x	x.x
		Mild	x	x.x	x	x.x	x	x.x	x	x.x	x	x.x	x	x.x	x	x.x	x	x.x	x	x.x
		Moderate	x	x.x	x	x.x	x	x.x	x	x.x	x	x.x	x	x.x	x	x.x	x	x.x	x	x.x
		Severe	x	x.x	x	x.x	x	x.x	x	x.x	x	x.x	x	x.x	x	x.x	x	x.x	x	x.x
	PT 2	Any Severity	x	x.x	x	x.x	x	x.x	x	x.x	x	x.x	x	x.x	x	x.x	x	x.x	x	x.x
		Mild	x	x.x	x	x.x	x	x.x	x	x.x	x	x.x	x	x.x	x	x.x	x	x.x	x	x.x
		Moderate	x	x.x	x	x.x	x	x.x	x	x.x	x	x.x	x	x.x	x	x.x	x	x.x	x	x.x
		Severe	x	x.x	x	x.x	x	x.x	x	x.x	x	x.x	x	x.x	x	x.x	x	x.x	x	x.x

N = Number of subjects in the Safety Population. For severity, a subject is counted once per preferred term and is summarized according to their highest severity. For vaccine-relatedness, a subject is only counted once per preferred term and is summarized according to their closest relationship.

14.3.2 Listing of Deaths, Other Serious and Significant Adverse Events**Table 30: Listing of Serious Adverse Events**

Adverse Event	Associated with Dose #	# of Days Post Associated Dose (Duration)	# of Days Post Dose the Event Became Serious	Reason Reported as an SAE	Severity	Relationship to Study Treatment	If Not Related, Alternative Etiology	Action Taken with Study Treatment	Subject Discontinued Due to AE	Outcome	MedDRA System Organ Class	MedDRA Preferred Term
Subject ID: , Treatment Group: , AE Number:												
Comments:												
Subject ID: , Treatment Group: , AE Number:												
Comments:												

Table 31: Listing of Vaccine-Related Medically Attended Adverse Events

Adverse Event	Associated with Dose No.	No. of Days Post Associated Dose (Duration)	Severity	Relationship to Study Treatment	If Not Related, Alternative Etiology	Action Taken with Study Treatment	Subject Discontinued Due to AE	Outcome	MedDRA System Organ Class	MedDRA Preferred Term
Subject ID: Treatment Group: AE Number:										
Comments:										
Subject ID: Treatment Group: AE Number:										
Comments:										

Table 32: Listing of Non-Serious, Unsolicited, Moderate or Severe Adverse Events

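### Medically attended adverse events are collected for 6 months whatever their cause, but only those judged vaccine-related are counted by arm

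*SAP*

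**What the plan says.** Both documents define the fourth primary outcome in the same way: "Frequency of Serious Adverse Events (SAEs) and vaccine-related Medically Attended Adverse Events (MAAEs) through 6 months post first vaccination" (SAP 3.2.1, Protocol 3.2.1). Protocol 11.4.2 and SAP 9.4 carry it into the analysis; SAP 9.4 states: "The number of SAEs and vaccine-related Medically Attended Adverse Events (MAAEs) through 6 months post first vaccination will be reported". The row for this outcome in SAP Table 23 is "At least one vaccine-related medically attended adverse event", and the supporting display is "Table 31: Listing of Vaccine-Related Medically Attended Adverse Events".

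The collection rule is wider. SAP 4.5.1, matching Protocol 9.1, names as a safety variable "Serious adverse events and MAAEs occurring from the time of study vaccination through approximately 6 months after the first study vaccination", with no condition on cause. Protocol 9.2.4 makes the investigator responsible for "recording all AE/SAEs/MAAEs that are observed or reported during this trial, regardless of the relationship to study product".

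The plan handles its other event classes differently. SAEs are counted in Table 23 and listed in Table 30 regardless of cause. For unsolicited AEs, the vaccine-related table (Table 27) is paired with a table of all such events by arm (Table 28).

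**The concern.** An event that the investigator calls unrelated drops out of the only displays that identify MAAEs. Attributing a non-serious illness weeks or months after a vaccination is uncertain even under a sound blind. A related-only count can therefore miss an imbalance between arms that nobody happened to attribute to vaccine, and it can show an imbalance that arises from differences in attribution. A count of subjects with any MAAE by arm does not depend on that judgement.

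This matters most after about Day 36, because no other non-serious events are collected then. At stake is how the late non-serious safety data of three boost schedules are described. No formal safety test is affected, because none is planned.

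**Working it through.** The documents give no event rate, power or alpha for safety, so there is no planned figure to reproduce. The check is of what is collected against what is displayed, followed by illustrations on assumed rates.

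**1. The late window.** Non-serious unsolicited AEs are collected to about 28 days after dose 2 (Protocol 9.3): Day 8 + 28 = Day 36. The calls at Days 76 and 106 (Protocol 7.3.4) and the Day 182 visit (7.4) collect only SAEs and MAAEs. The late window is 182 − 36 = 146 days, out of 182 − 1 = 181 days of follow-up: 146/181 = 81%. Dose 2 may be given up to Day 10, which moves the boundary to Day 38 and the share to 144/181 = 80%. This is a share of time, not of events.

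**2. Where an MAAE judged unrelated can appear.**
- Table 23 (MAAE row) and Table 31: excluded.
- Table 28: all unsolicited AEs by arm, with no MAAE label. SAP 9.3.2 describes it as corresponding to Table 27, whose events end 28 days after dose 2.
- Table 29: related, not related and total by arm. No MAAE label and no window of its own.
- Table 32: non-serious moderate or severe events only. No MAAE label and no window stated.
- Figures 9 to 12: split by relationship. No MAAE label and no late window stated.
- Listing 12: has columns for SAE status, days after dose and relationship, but none for MAAE, and states no window.

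SAP 4.5.1 also ties unsolicited AEs to 28 days after dose 2. None of these displays gives the number of subjects per arm with any MAAE.

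**3. What the filter can hide with equal attribution in both arms.** Assume at most one MAAE per subject, independent subjects, 10% of MAAEs called related in each arm, and all-cause risks of 10% and 30%. Expected all-cause counts are 20 × 0.10 = 2 and 20 × 0.30 = 6. Expected related counts are 0.2 and 0.6. The chance of no related event is (1 − 0.01)^20 = 0.82 in one arm and (1 − 0.03)^20 = 0.54 in the other, so the row reads 0 against 0 with probability 0.818 × 0.544 = 0.44.

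**4. What differential attribution can create.** Assume the same 20% MAAE risk in both arms, so 4 expected per 20 in each. With 10% called related after the placebo boost, the expected related count there is 0.4. If 10%, 20%, 30% or 50% are called related after an active boost, the expected related count is 0.4, 0.8, 1.2 or 2.0. The gap runs from none to fivefold while the all-cause count stays at 4 against 4.

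**5. Could post-boost reactions inform attribution?** Protocol 2.3.1 reports fever in 38.1% at the equivalent ChAd3 dose against 5% in controls (Phase 1), and adult injection-site pain in 47.6% against 7.6% (Phase 2). The prior probability of an active boost is 2/3. By Bayes' rule, P(active | fever) = (2/3 × 0.381) / (2/3 × 0.381 + 1/3 × 0.05) = 0.94, and P(active | no fever) = (2/3 × 0.619) / (2/3 × 0.619 + 1/3 × 0.95) = 0.57. For pain the figures are 0.93 and 0.53. This assumes that either active boost behaves like a first ChAd3 dose in other studies; the documents give no rates for this schedule.

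**6. Precision.** With 20 per arm, 0/20 has an exact 95% upper limit of 16.8%, and 4/20 has limits of 5.7% and 43.7%. Any count, related or all-cause, is descriptive.

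**The case against.** **The filter is the pre-specified outcome.** Related-only MAAE is stated consistently in both documents and in the protocol's analysis section. A reader might infer that the SAP departs from the protocol; it does not. Nor does the protocol's sentence in 9.2.1, "Whether the AE is related or not, is not a factor in determining what is or is not reported in this trial", settle the matter. It governs what sites record, and the plan meets it because all MAAEs are recorded.

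**Late safety does not rest on relatedness alone.** It would be wrong to call the period after Day 36 unreported. SAEs are counted by arm and listed regardless of cause through 6 months, and related MAAEs are reported too. The point is confined to non-serious late events.

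**Unrelated MAAEs are not lost.** An MAAE is by definition an unsolicited AE, so it can appear in the displays in step 2. After about Day 36 a non-serious event in Listing 12 should be an MAAE by construction, so a reader could count late ones by arm by hand. That stands if Listing 12 runs to Day 182, which is not stated. It does not help with MAAEs before Day 36, which cannot be told apart from other unsolicited AEs.

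**Unblinding is not shown.** A reader might infer that investigators will know the arm. The documents do not support that. Assessors are blinded, syringes are masked, and an unblinded administrator gives the injection and makes no assessments. The rates in step 5 are first-dose data, and one study had 25.0% Grade 1 pain on placebo. All arms received ChAd3 on Day 1, so a late event can be called related in any arm. Partial functional unblinding is plausible and no more.

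**Conclusion.** The point holds as a design weakness in the displays, not as an error or a contradiction. No arm-level count of subjects with any MAAE is planned, and the late non-serious safety summary depends on investigator attribution. The plan avoids that dependence for SAEs and for unsolicited AEs.

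The size of any distortion cannot be computed from the documents. Steps 3 and 4 rest wholly on assumed MAAE risks and attribution rates, and with no difference in attribution step 4 shows no spurious gap. Step 3 does not need unblinding at all, and that makes the case for an all-cause row without relying on step 5. Numbers will be small either way. This is worth doing because it is cheap and makes the display complete; the primary outcome itself does not need to change.

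**What to change.** Before unblinding:
- Keep the vaccine-related MAAE row in Table 23 as the primary outcome, and add beneath it a row *At least one MAAE (any relationship)* by arm with n and %.
- Widen Table 31 to all MAAEs and retitle it. It already has a relationship column, and its column for alternative etiology of unrelated events would then have a use. Alternatively, add an MAAE flag to Listing 12.
- Amend SAP 9.4 to match, and state the time window for Tables 28, 29 and 32 and Listing 12.
- In the same edit, correct the Table 23 footnotes, which send the reader to Tables 28 and 29 for SAEs and MAAEs instead of Tables 30 and 31.

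The cost is one table row and a wider listing filter on data already collected. The downside is a longer listing that includes incidental illness. Sample size and the primary outcome do not change.

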9.5. Pregnancies

Efforts will be made to follow all pregnancies reported during the course of the study to pregnancy outcome pending the subject's permission. An individual data listing of pregnancy reports detected will be provided in [Listing 18](#), [Listing 19](#), [Listing 20](#), [Listing 21](#), and [Listing 22](#).

9.6. Clinical Laboratory Evaluations

Clinical safety laboratory adverse event gradings are presented in [Table 9](#) and [Table 10](#). Safety laboratory parameters and toxicity grade criteria are summarized in [Table 9](#) and [Table 10](#). Unscheduled or repeated follow-up tests for medical or safety reasons will be listed but excluded from per-visit tabular and graphical summaries. These results will be included when summarizing maximum response from baseline.

For baseline laboratory results that are abnormal according to the local laboratory reference range (see protocol Appendix C) and fall within Grade 1 toxicity table range, these will not be considered laboratory adverse event (AE) and will thus not be graded. However, if baseline clinical labs fall within Grade 1 range, then a laboratory AE is reported only if the value changes such that it falls into Grade 2 or higher when subsequent safety laboratory testing is done.

Listings of abnormal laboratory results will be provided as shown in [Table 33](#) and [Table 34](#). For each laboratory parameter, the following summaries will be generated for each treatment group:

- Laboratory AEs from the time of first study vaccination through approximately 28 days after the second vaccination will be summarized by severity grade (none, mild, moderate, severe) for each laboratory visit using percentages and exact two-sided 95% CIs ([Table 35](#)).
- A tabular summary of descriptive statistics including the mean, standard deviation, median, minimum, and maximum for per-visit results ([Table 36](#)).
- A tabular summary of descriptive statistics including the mean, standard deviation, median, minimum, and maximum for fold change compared to pre-vaccination ([Table 37](#)).
- A graphical summary of change from baseline ([Figure 13](#)).

[Listing 13](#) and [Listing 14](#) will provide a complete listing of individual clinical laboratory results.

9.7. Vital Signs and Physical Evaluations

Vital sign severity grading criteria can be found in [Table 8](#). Vital sign measurements included oral temperature, systolic and diastolic blood pressure and heart rate assessed at Screening, Days 1 and 8. Vital signs will be tabulated by maximum severity grade (none, mild, moderate, severe) and study day, for each treatment group separately, overall and by vital sign variable ([Table 38](#)). Individual data listings of vital signs and physical exam findings will be provided in [Listing 15](#) and [Listing 16](#), respectively.

